2.2. Periodontal diagnosis, treatment and probiotic exposure definition

Periodontal diagnosis and stage/grade assignment were established according to the 2017 World Workshop classification of periodontal diseases and conditions (Papapanou et al., 2018; Tonetti et al., 2018). Only patients with Stage III Grade B periodontitis were included. Periodontitis was defined by detectable interdental CAL at two or more non-adjacent teeth. Stage III Grade B periodontitis was defined by interdental CAL ≥ 5 mm at the site of greatest loss, with grading based on a bone loss/age ratio of 0.25–1.00.

All patients received routine NSPT, including individualized oral hygiene instruction and supra- and subgingival mechanical debridement/root surface instrumentation where indicated (Herrera et al., 2020; Suvan et al., 2020). All NSPT procedures were performed by the same periodontist ([name]).

The study did not include an investigator-assigned probiotic intervention. No probiotic strain, dose, formulation, frequency, duration or adherence protocol was prescribed as part of the study. Group classification was based on self-reported use of probiotic supplements or commercially labelled probiotic products during active periodontal treatment and post-treatment follow-up. Patients who reported such use were classified as probiotic product users, whereas those reporting no probiotic supplement or commercially labelled probiotic product use during the same interval were classified as non-users. Traditional homemade fermented foods, including homemade yogurt, kefir, pickles, vinegar, sourdough products and boza, were recorded as dietary fermented-food habits when reported but were not used to define probiotic exposure because strain composition, colony-forming unit content, microbial viability, dose and consistency of intake could not be verified (FAO/WHO, 2002; Hill et al., 2014; Sahin, 2026). Therefore, the exposure represented self-reported real-world probiotic-labelled product use rather than standardized probiotic intake.

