2.3. Clinical assessment

Clinical periodontal measurements including PI, BOP, PPD, CAL were performed at baseline, 1 month, and 3 months after NSPT by a calibrated examiner ([name]) who was not involved in treatment delivery and was blinded to participants' probiotic product-use status and questionnaire responses. Participants were instructed not to disclose their probiotic product use during clinical examinations. Probiotic product-use data and questionnaire responses were recorded separately from the clinical examination forms and were linked to the clinical dataset only after completion of all follow-up measurements.

Before study initiation, examiner calibration was performed in 10 volunteers who were not included in the study. Probing pocket depth and clinical attachment level measurements were repeated at six sites per tooth, and intra-examiner reproducibility was assessed. The calibrated examiner demonstrated high reproducibility, with a κ value of 0.896, and repeated measurements differed by no more than 1 mm at 90% of sites.

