2.4. Questionnaire and patient-reported assessment

At baseline, participants completed a structured questionnaire including demographic and health-related information, previous periodontal treatment history, probiotic knowledge/familiarity, attitudes toward probiotic use in periodontal therapy, previous probiotic exposure and probiotic form/source preferences. The questionnaire framework was adapted from previously used probiotic knowledge and consumption surveys and from the approved study protocol (Patait et al., 2022; Sahin, 2026; Wang et al., 2025).

Baseline probiotic knowledge/familiarity was assessed using items related to prior awareness of the term "probiotic", self-rated knowledge level, correct identification of the probiotic definition and perceived general probiotic benefit. These variables were additionally combined into an exploratory baseline knowledge/familiarity index.

Attitudes toward probiotic use in periodontal therapy were assessed using Likert-type items addressing perceived periodontal benefit, willingness to use probiotics as part of periodontal treatment, confidence in probiotic use if recommended by a dentist and ease of acceptance when adequate explanation was provided. A high acceptance profile was defined a priori as agreement or strong agreement with at least three of four predefined attitude items.

The questionnaire also included items on product and formulation preferences, including preferred supplement formulation, commercially labelled probiotic product type and preferred route/form of use. Traditional homemade fermented foods were recorded only as dietary fermented-food habits and were not used to define exposure. These items were used descriptively to characterize patient preferences and were not used to define a standardized probiotic exposure.

OHRQoL was assessed using the Turkish version of the Oral Health Impact Profile-14 (OHIP-14-TR) at baseline, 1 month and 3 months (Mumcu et al., 2006; Slade, 1997). Each item was scored on a 5-point Likert scale, and total scores ranged from 0 to 56, with higher scores indicating poorer OHRQoL. At follow-up, additional patient-reported measures included self-rated current oral health, perceived change in oral problems since treatment, overall treatment satisfaction and future willingness to use probiotics if recommended. Among probiotic product users, probiotic-related experience was also recorded, including satisfaction with probiotic use and self-reported adherence.

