2.5. Statistical analysis

All statistical analyses were performed using IBM SPSS Statistics version 30.0 (IBM Corp., Armonk, NY, USA). Continuous variables were expressed as mean \pm standard deviation or median [interquartile range], as appropriate, and categorical variables as number and percentage. Baseline comparisons between probiotic product users and non-users were performed using the independent-samples t test or Mann-Whitney U test for continuous variables and the chi-square test or Fisher's exact test for categorical variables.

Clinical outcomes and OHIP-14 total scores at 1 and 3 months were analyzed using regression models adjusted for age, sex, current smoking status, education level, previous periodontal treatment and the baseline value of the corresponding outcome. Current smoking was coded as current smoking versus non-current smoking. Continuous outcomes, including PI, mean PPD, CAL, BOP and OHIP-14 total score, were analyzed using linear regression

models. Count outcomes, including the number of sites with PPD ≥ 5 mm, were analyzed using generalized linear models with a log link and expressed as rate ratios with 95% confidence intervals. Additional sensitivity models included previous probiotic recommendation and prior familiarity with the term “probiotic”.

Within-group changes in clinical and OHRQoL outcomes across baseline, 1 month and 3 months were analyzed using the Friedman test. Questionnaire-based probiotic knowledge/familiarity, attitude, acceptance, preference, satisfaction and adherence-related variables were analyzed according to item type using the chi-square test, Fisher’s exact test, Mann–Whitney U test or Wilcoxon signed-rank test, as appropriate. Factors associated with reported probiotic product use were evaluated using multivariable logistic regression. A two-sided p value <0.05 was considered statistically significant.

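### OHIP-14 is self-reported by patients who know their product use, and baseline perceived periodontal benefit, a plausible confounder, is in neither the main nor the sensitivity models

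*Combined protocol and SAP*

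**What the plan says.** **Exposure.** Section 2.2 states: "The study did not include an investigator-assigned probiotic intervention". It continues: "Group classification was based on self-reported use of probiotic supplements or commercially labelled probiotic products during active periodontal treatment and post-treatment follow-up". Patients therefore chose the product and know whether they take it.

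**Blinding.** Section 2.3 says that the examiner who records PI, BOP, PPD and CAL "was blinded to participants' probiotic product-use status and questionnaire responses". No corresponding protection is described, or possible, for what patients report about themselves.

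**Outcome.** OHIP-14 is completed by the patient at baseline, 1 month and 3 months. On its scoring, section 2.4 says: "Each item was scored on a 5-point Likert scale, and total scores ranged from 0 to 56, with higher scores indicating poorer OHRQoL".

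**Belief measured at baseline.** According to section 2.4, the baseline questionnaire covers "attitudes toward probiotic use in periodontal therapy, previous probiotic exposure and probiotic form/source preferences". The attitude block has "Likert-type items addressing perceived periodontal benefit, willingness to use probiotics as part of periodontal treatment", together with confidence if a dentist recommends use and ease of acceptance after explanation. Agreement with at least three of the four items defines a high acceptance profile. A separate item on general probiotic benefit sits in the knowledge/familiarity set.

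**Models.** Section 2.5 adjusts the OHIP-14 models for age, sex, current smoking, education, previous periodontal treatment and the baseline score. It then says: "Additional sensitivity models included previous probiotic recommendation and prior familiarity with the term" probiotic. Attitude and acceptance variables are analysed by item-level tests. A logistic model for product use is planned, with its covariates unlisted.

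**The concern.** A patient who believes at baseline that probiotics help the gums may be more likely to use one, and may also rate oral health more favourably after treatment whatever the product does. If both links exist, the belief confounds the user versus non-user contrast in OHIP-14 and part of the difference would be wrongly credited to the product.

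The plan already recognises a need to test robustness to probiotic-related background variables, but the two it chose do not capture this belief directly. A person can know the word and doubt any periodontal benefit. A previous recommendation may carry some expectation with it, but it is not a measure of the patient's own view. A user coefficient that barely moves in the planned sensitivity models would therefore say little about attitude, although readers could take it as reassurance. The item that asks the question directly has been collected and is unused in the outcome models.

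**Working it through.** **1. The plan's own figure.** Section 2.1 gives d = 0.50, two-sided α = 0.05 and 80% power. n per group = 2(1.960 + 0.842)² / 0.50² = 62.8, so 63, as stated (a t-based calculation gives 64). At the 65 per group analysed, normal-approximation power is 81%.

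**2. Which models contain the belief item.**

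| Analysis in section 2.5 | Perceived periodontal benefit included? |
|---|---|
| Main OHIP-14 models, 1 and 3 months | No |
| Sensitivity models | No |
| Item-level tests of attitude variables | Yes, but these do not adjust OHIP-14 |
| Logistic model for product use | Not stated; would not adjust OHIP-14 in any case |

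**3. Bias if belief shifts OHIP-14 equally in users and non-users.** The documents give no belief shares by group, no link between belief and OHIP-14, and no OHIP-14 SD, so all inputs here are assumptions. Suppose 70–80% of users and 30–40% of non-users agree with the item (gap 0.30 to 0.50), and belief shifts follow-up OHIP-14 by 0.2 to 0.5 SD.

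Spurious difference = gap × belief effect. SE = √(2/65) = 0.175 SD. With no true product effect, the two-sided rejection rate of a t-test is:

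| Gap × effect | Spurious difference (SD) | False-positive rate |
|---|---|---|
| 0.30 × 0.2 | 0.06 | 6.3% |
| 0.30 × 0.5 | 0.15 | 13.6% |
| 0.50 × 0.5 | 0.25 | 29.3% |

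Wider assumptions widen the range (normal approximation): a 10-point gap with 0.2 SD gives 0.02 SD and 5.1%; a 40-point gap with 0.8 SD gives 0.32 SD and 44.6%. The belief effect must be read as what remains after the planned covariates, including baseline OHIP-14. If those absorb much of it, the low end applies.

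**4. What adjustment can and cannot remove.** Suppose instead that expectation acts only in believers who take a product, shifting their score by b. With p₁ the share of believers among users and p₀ among non-users, the unadjusted spurious difference is p₁b. Adding belief as a main effect gives a weighted average of b (believers) and 0 (non-believers), with weights

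- believers: p₁p₀/(p₁ + p₀)
- non-believers: (1 − p₁)(1 − p₀)/(2 − p₁ − p₀)

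At 75% and 35% the weights are 0.239 and 0.181. The adjusted difference is 0.239/(0.239 + 0.181) × b = 0.57b, against 0.75b unadjusted. Over the assumed shares, 0.50b to 0.64b remains of 0.70b to 0.80b, so only 20–29% is removed.

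**5. Cost in precision.** For a binary belief covariate and equal groups, r² = gap² × 0.25 / [p(1 − p)], with p the overall share, and variance inflation = 1/(1 − r²).

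- 70% vs 40%: r² = 0.09 × 0.25/0.2475 = 0.091; inflation 1.10; power at d = 0.50 is 78%.
- 80% vs 30%: r² = 0.25 × 0.25/0.2475 = 0.253; inflation 1.34; power is 69%.

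Both are before any gain from lower residual variance.

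**The case against.** The strongest objection is that the adjustment mostly misses the mechanism that comes first to mind. If the worry is that patients report better because they know they take something, a baseline attitude covariate does little, as step 4 shows. The difference would then tend to persist after adjustment and could give false comfort. This stands, and it limits what the added model may be used to claim.

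Several further points also stand:

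- Adjustment for baseline OHIP-14 and education should absorb part of any stable difference in how patients rate themselves. It does not cover expectation that alters reporting after treatment.
- Previous recommendation is more than awareness and may carry some expectation.
- The high acceptance profile is a poor proxy for belief. Three of its four items concern willingness, confidence if a dentist recommends use, and acceptance, so a patient can meet it without agreeing that probiotics help the gums.
- Perceived periodontal benefit is not the only belief item, since general probiotic benefit is also recorded. That item is not named in any outcome model either.

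The study is observational, and section 2.1 says that its sample-size calculation is not meant to support causal inference. That tempers interpretation, but it concerns the calculation and supplies no adjustment.

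A reader might infer more: that an OHIP-14 advantage in users would simply be expectation, or that attitude probably drove product use. The documents support neither. They give no attitude data by group and no association with OHIP-14. Nor do they support the opposite inference, that a difference surviving adjustment has been cleared of reporting bias.

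**Conclusion.** The gap is real and worth closing. That patients know their exposure, that OHIP-14 is self-reported outside the blinding, that perceived periodontal benefit was collected at baseline, and that no stated outcome model includes it can all be read directly from sections 2.2 to 2.5. That the item confounds the contrast is plausible, not shown.

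The size is unknown. It is negligible if belief is weakly tied to use or to OHIP-14, and material if both ties are strong. The rates in step 3 rest wholly on assumed shares and effects, and come from a simple two-group comparison rather than the planned adjusted model. The point concerns pre-existing attitude only. Reporting bias from knowing one's exposure remains whatever covariates are added, and has to be handled in interpretation.

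**What to change.** 1. Add the baseline perceived-periodontal-benefit item to the OHIP-14 sensitivity models at 1 and 3 months, in preference to the high acceptance profile. Leave the main models as they are.
2. Report the user coefficient and its 95% confidence interval with and without the item, and the item's distribution by group, so that readers can see which part of the assumed range applies.
3. Label the model post hoc if outcomes have already been seen. The text is in the past tense and describes a final analytic sample of 130, so this may well be the case.
4. State that the model addresses pre-existing attitude only. Read any persisting OHIP-14 difference against the examiner-blinded PI, BOP, PPD and CAL results, and give the residual reporting bias as a limitation.

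The cost is one more covariate from data already collected. Under the assumed 30- to 50-point gaps, precision falls as in step 5, in the sensitivity model only; a wider interval there should not by itself be read as loss of the effect.

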2.1. Study design and participants

This prospective observational study was conducted at the Department of Periodontology, Faculty of Dentistry, Istanbul Medipol University. The study was approved by the ethics committee of Istanbul Medipol University in accordance with the Declaration of Helsinki (World Medical Association, 2013) (Decision No: 1553; Date: 11 December 2025). The study was reported in accordance with the Strengthening the Reporting of Observational Studies in Epidemiology (STROBE) statement (von Elm et al., 2007). Written informed consent was obtained from all participants before enrollment, and participation was voluntary without any effect on periodontal treatment.

Sample size estimation was based on the 3-month deep-pocket PPD difference reported by Teughels et al. (2013) (SRP + probiotic: 2.88 ± 0.35 mm; SRP + placebo: 2.25 ± 0.27 mm). Using a conservative standardized effect size of 0.50, a two-sided α of 0.05 and 80% power, at least 63 patients per group were required; therefore, 65 patients were included in each group. Because the present study was observational and exposure was not investigator-assigned, this calculation was used to estimate an adequate minimum group size for detecting clinically relevant between-group differences rather than to support causal inference.

Patients scheduled to undergo NSPT were consecutively screened for eligibility at the periodontal clinic. Of 184 patients screened, 140 eligible patients were enrolled after pre-enrollment exclusions, and 130 patients who completed the required follow-up assessments were included in the final analysis. Eligible participants were 18–70 years of age, had at least 20 natural teeth, were diagnosed with Stage III Grade B periodontitis and were available for baseline, 1-month and 3-month evaluations. Patients were excluded if they had used systemic antibiotics within the previous 3 months, had received periodontal treatment within the previous 6 months, had systemic disease, were pregnant or lactating, or had severe cognitive or psychiatric conditions that could interfere with questionnaire completion or follow-up. Current smoking status was recorded at baseline and was not used as an exclusion criterion.

The final analytic sample comprised 65 patients in the probiotic product-use group and 65 patients in the non-user group.

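### Existing and new probiotic users can be pooled, and previous exposure, although collected at baseline, enters no outcome model; if prior use had already changed baseline values, baseline adjustment removes part of the association

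*Combined protocol and SAP*

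**What the plan says.** Section 2.2 fixes exposure by a time window: "Group classification was based on self-reported use of probiotic supplements or commercially labelled probiotic products during active periodontal treatment and post-treatment follow-up". Anyone reporting use in that window is a user ("Patients who reported such use were classified as probiotic product users"), and the comparator is the mirror image: patients reporting "no probiotic supplement or commercially labelled probiotic product use during the same interval were classified as non-users". The date of first use plays no part in either definition.

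The exclusions in section 2.1 cover other recent treatments ("Patients were excluded if they had used systemic antibiotics within the previous 3 months, had received periodontal treatment within the previous 6 months") as well as systemic disease, pregnancy or lactation, and severe cognitive or psychiatric conditions. Earlier probiotic use is not among them, and no washout is set.

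According to section 2.4, the baseline questionnaire covers "previous probiotic exposure and probiotic form/source preferences".

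The outcome models in section 2.5 are "adjusted for age, sex, current smoking status, education level, previous periodontal treatment and the baseline value of the corresponding outcome". The sensitivity models are described thus: "Additional sensitivity models included previous probiotic recommendation and prior familiarity with the term" probiotic. Section 2.5 also has a model of who uses products ("Factors associated with reported probiotic product use were evaluated using multivariable logistic regression"); its predictors are not listed and it is not an outcome model.

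**The concern.** In a patient who was already taking a product, PI, BOP, PPD, CAL and OHIP-14 at baseline are measured under exposure. If the product had already moved those values, conditioning on them takes out the part of the group difference that was there before NSPT. The reported coefficient is then a blend of two quantities: the association with starting a product around NSPT, and the further difference seen in people who were using one anyway. A reader cannot separate them.

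Former users in the comparator add a second source of blurring, and long-term users may differ from new users in health behaviour. These could shift the estimate in either direction.

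The variable that bears most directly on this was collected. The two covariates chosen for the sensitivity models do not replace it: a patient can know the term, or have been given a recommendation, without ever having taken a product.

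**Working it through.** **1. The plan's own figure.** Inputs from section 2.1: standardized effect 0.50, two-sided α 0.05, power 80%. By normal approximation, n per group = 2 × (1.960 + 0.842)² / 0.50² = 62.8, so 63. This matches the plan and is not in dispute.

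**2. Where prior use appears.**

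- User and non-user definitions (2.2): no reference to use before treatment.
- Eligibility (2.1): no exclusion or washout for it.
- Baseline questionnaire (2.4): collected.
- Main outcome models (2.5): absent.
- Sensitivity outcome models (2.5): absent; recommendation and familiarity only.

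So the definitions permit pooling, and nothing in the outcome analysis separates the two kinds of user.

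**3. Size of the loss if the mechanism operates.** Let d be the 3-month difference between users and non-users, taken as equal for new and continuing users. Let q be the share of users already using at baseline, f the fraction of d already present in them at baseline, and b the slope of the 3-month value on the baseline value. Non-users are taken to have no carried-over effect.

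- Baseline difference between groups = q × f × d.
- Baseline-adjusted difference = d − b × (q × f × d) = d × (1 − b × q × f).
- Fraction removed = b × q × f.

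The documents give none of b, q or f, so all three are assumed. With the plan's d = 0.50 SD:

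| b | q | f | Fraction removed | Remaining difference (SD) |
|---|---|---|---|---|
| any | 0 | any | 0 | 0.500 |
| any | any | 0 | 0 | 0.500 |
| 0.5 | 25% | 0.5 | 6.25% | 0.469 |
| 0.7 | 50% | 0.5 | 17.5% | 0.413 |
| 0.5 | 25% | 1 | 12.5% | 0.438 |
| 0.7 | 25% | 1 | 17.5% | 0.413 |
| 0.5 | 50% | 1 | 25% | 0.375 |
| 0.7 | 50% | 1 | 35% | 0.325 |

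**4. Check by simulation.** With 200,000 patients per group, f = 1 and equal SDs at the two visits, the baseline-adjusted difference was 0.378 at b = 0.5, q = 50% (formula 0.375) and 0.331 at b = 0.7, q = 50% (formula 0.325). Adding a term for use at baseline, or restricting to new users versus non-users, returned 0.49 to 0.50 in every scenario. That term identified use at baseline exactly; an item that only separates never from ever would do less well.

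**The case against.** **The mixing is possible, not shown.** A reader might infer that the user group is known to contain continuing users. The documents give no count of patients using products before NSPT; the definitions only allow it. This stands, and the point is worded accordingly.

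**f = 1 is the extreme case.** The plan's effect size is tied to a 3-month comparison of SRP plus probiotic with SRP plus placebo, that is, an effect on top of instrumentation. Nothing in the documents says a similar effect exists in untreated pockets. This also stands, and is why the table includes f = 0 and f = 0.5.

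**Loss of power.** A reader might set the shrunken differences against 65 per group and conclude that power falls well below the planned level. With the unadjusted SD, b = 0.7 and q = 50% would give 46%, against 81% for d = 0.50. That is inconsistent: it uses the baseline slope to shrink the effect but ignores the variance the same baseline explains. With equal SDs at both visits (assumed), the residual SD is √(1 − b²), or 0.87 at b = 0.5 and 0.71 at b = 0.7. Power at 65 per group is then about 82% to 91% at q = 25% and 69% to 74% at q = 50%, against 91% to 98% with no continuing users. Even these figures rest wholly on assumed inputs, so no power forecast belongs in the point.

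**The sensitivity covariates.** It is tempting to add that recommendation and familiarity only cost precision and should be dropped. The documents do not support that: both could stand in for selection into use, and being confined to sensitivity models they cost the main estimate nothing.

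**The estimand is deliberate.** Section 2.2 describes exposure as real-world use of labelled products, and section 2.1 disclaims causal inference. That disclaimer concerns the sample-size calculation. It softens the word effect, but an adjusted association that mixes starting with continuing is no easier to interpret.

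**Conclusion.** The point holds as a gap in the sensitivity analyses. The definitions and eligibility criteria let continuing users be pooled with new users and former users be counted as non-users, and a variable collected at baseline that bears on this enters no outcome model.

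The consequence is conditional. If prior use had already changed baseline values, a fraction b × q × f of the association is adjusted away: nothing if q or f is zero, and about 12% to 35% for b = 0.5 to 0.7, q = 25% to 50% and f = 1. These inputs are assumptions, and the range is not an estimate for this study. The formula also assumes that new and continuing users share the same 3-month difference and that former users carry nothing over. Without those assumptions even the direction of the net shift is not fixed.

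**What to change.** In section 2.5:

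1. Report previous probiotic exposure by group with the other baseline comparisons.
2. Add it, in the form recorded, to the sensitivity outcome models alongside previous recommendation and familiarity with the term, and keep those two.
3. If the item identifies use at baseline, add a sensitivity analysis of new users versus non-users that excludes anyone using a product at baseline. Section 2.4 does not say whether past and current use are distinguished; if they are not, state that as a limitation.

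Section 2.1 reports completed follow-up and a final sample, so label these analyses post hoc if the data have already been analysed.

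The cost is mainly wording, since section 2.4 already collects previous exposure. The downside is a smaller sample and lower precision in the new-user comparison.

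### No adjusted analysis is planned for follow-up willingness or treatment satisfaction, so a user versus non-user difference cannot be separated from who chose to use a product

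*Combined protocol and SAP*

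**What the plan says.** **Groups.** Section 2.2 states that "The study did not include an investigator-assigned probiotic intervention" and that "Group classification was based on self-reported use of probiotic supplements or commercially labelled probiotic products during active periodontal treatment and post-treatment follow-up". Section 2.1 gives 65 patients analysed in each group.

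**Baseline items.** Section 2.4 puts attitude items in the baseline questionnaire, including "willingness to use probiotics as part of periodontal treatment, confidence in probiotic use if recommended by a dentist".

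**Follow-up items.** The same section adds self-rated oral health and "perceived change in oral problems since treatment, overall treatment satisfaction and future willingness to use probiotics if recommended". Satisfaction with probiotic use and adherence are recorded in users only, so they involve no comparison between groups.

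**Analysis.** Section 2.5 says "Clinical outcomes and OHIP-14 total scores at 1 and 3 months were analyzed using regression models adjusted for age, sex, current smoking status", with education, treatment history and the baseline value of the outcome as further covariates. For the remaining questionnaire variables it says "Questionnaire-based probiotic knowledge/familiarity, attitude, acceptance, preference, satisfaction and adherence-related variables were analyzed according to item type using the chi-square test", with Fisher, Mann-Whitney and Wilcoxon signed-rank tests as the alternatives. The sensitivity models add earlier probiotic recommendation and familiarity with the term. The logistic regression has product use as its outcome.

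**The concern.** Patients who are more willing at baseline may well be more likely to become users. The documents do not report this, but it is a plausible route into a self-selected group. Willingness is asked about at baseline and again, in different words, at follow-up. If the groups differ at baseline, some of that gap will persist even when using a product changes nothing, and an unadjusted test will register it.

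Overall treatment satisfaction was not measured at baseline, so nothing can carry over in the same way. The issue there is consistency. The plan adjusts OHIP-14, another patient-reported outcome in the same patients, for measured differences between the groups. It gives no reason for leaving satisfaction unadjusted.

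What is at stake is the interpretation of these secondary patient-reported comparisons. The clinical and OHIP-14 analyses are not affected.

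**Working it through.** **1. The plan's own figure.** Section 2.1 gives 63 per group for a standardised effect of 0.50, two-sided α 0.05 and 80% power. By the normal formula, n = 2 × (1.960 + 0.842)² / 0.50² = 62.8, so 63. The figure reproduces. Power with 65 per group is 0.813 (normal) or 0.808 (t). The sample size is not in dispute; 65 per group is carried forward.

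**2. Which analysis reaches which item.**

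| Follow-up item | Baseline counterpart | Named in the test sentence of 2.5? | Adjusted model? |
|---|---|---|---|
| OHIP-14 total | Yes | No, has its own model | Yes |
| Future willingness | Yes, similar item | By inference (attitude, acceptance) | No |
| Overall treatment satisfaction | No | Probably (satisfaction) | No |
| Perceived change | No | No | No |
| Self-rated oral health | None described | No | No |

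The sensitivity models do not include willingness, and no text extends them to questionnaire items. The logistic model does not adjust these comparisons, because product use is its outcome. The Wilcoxon signed-rank test is paired within patients and does not remove a baseline difference between groups.

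**3. Carry-over for willingness.** Let d be the baseline gap in SD units and r the baseline to follow-up correlation, with no effect of use. The documents give neither, so both are assumptions. On a continuous scale with unit within-group SD, the expected follow-up gap is r × d, with standard error √(2/65) = 0.175. For d = 0.5 and r = 0.5 the gap is 0.25 SD, and 0.25 / 0.175 = 1.43. The chance of rejection is about Φ(1.43 − 1.96) = 0.30; the t-based value is 29.3%.

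**4. Simulation.** A latent normal variable was cut to a 5-point item, with 65 per group and 2,000 studies per cell. Chi-square is on agree versus not. The adjusted test is linear regression on group plus the baseline item.

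| d | r | r × d | t-based, continuous | Mann-Whitney | Chi-square | Adjusted |
|---|---|---|---|---|---|---|
| 0.3 | 0.3 | 0.09 | 8.0% | 7.0% | 6.3% | 4.8% |
| 0.3 | 0.5 | 0.15 | 13.6% | 11.9% | 9.2% | 5.4% |
| 0.3 | 0.7 | 0.21 | 22.1% | 19.2% | 14.9% | 5.4% |
| 0.5 | 0.3 | 0.15 | 13.6% | 11.9% | 8.8% | 5.3% |
| 0.5 | 0.5 | 0.25 | 29.3% | 24.9% | 18.6% | 4.5% |
| 0.5 | 0.7 | 0.35 | 50.8% | 45.3% | 33.0% | 5.3% |
| 0.8 | 0.3 | 0.24 | 27.4% | 24.2% | 17.3% | 5.6% |
| 0.8 | 0.5 | 0.40 | 61.9% | 56.6% | 42.6% | 5.6% |
| 0.8 | 0.7 | 0.56 | 88.7% | 85.8% | 73.9% | 6.4% |

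With d = 0 every test rejects in 4.3% to 5.3% of studies, so the excess comes from the baseline gap.

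The Monte Carlo standard error at 7% is √(0.07 × 0.93 / 2000) = 0.6 percentage points. Repeat simulations of the same design gave Mann-Whitney rates of 8% (0.3/0.3), 26% (0.5/0.5) and 84% to 86% (0.8/0.7), with linear adjustment at 5% to 8%. An ordinal model in 300 runs gave roughly 6% to 9%; so few runs do not settle its exact error rate.

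**5. Satisfaction.** No magnitude was computed. The carry-over model needs a baseline value, and this item has none.

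**The case against.** The strongest reply is about scope. The test sentence does not say that it compares groups, gives no time point, and names neither willingness, perceived change nor self-rated oral health. Attitude and acceptance are introduced as baseline constructs, and satisfaction and adherence appear together as users-only items. It could therefore be read as covering little at follow-up. This stands in part: willingness is included only by inference, and for perceived change and self-rated oral health the documents support no more than that the analysis is unspecified. But on either reading no adjusted model covers any of these items.

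Second, the simulated rejections are errors only if the difference is taken as an effect of use. If users are more willing at follow-up, the unadjusted test correctly detects an association. That stands. A reader might infer that the plan attributes willingness to product use, or that a question about acceptance cannot be answered. The documents state neither a causal reading of these items nor such a question, and a descriptive comparison remains possible. The caution about causal inference in Section 2.1 is attached to the sample size calculation, so it does not label these results either.

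Third, both inputs are assumed, the range is wide, and the baseline and follow-up items are worded differently. That stands, so the simulation is an illustration.

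Fourth, the baseline comparisons in Section 2.5 may show an attitude imbalance. Showing it helps the reader but does not remove it from the follow-up comparison.

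**Conclusion.** The concern holds in a limited form. Adjustment is planned for clinical outcomes and the OHIP-14 total only, although the groups are self-selected and baseline willingness is collected.

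- **Future willingness:** a user versus non-user difference cannot be separated from a pre-existing one. With no effect of use, the unadjusted rejection rate is about 8% to 86% over the assumed range and about 25% at its centre (d = 0.5, r = 0.5). Linear adjustment for the baseline item gives about 5% to 8%. This rests on the assumed d and r, and on reading willingness as an attitude or acceptance variable.
- **Overall treatment satisfaction:** confounding is possible and left unadjusted, but its size is not estimated. A reader might infer that the willingness figures apply here too; they do not.
- **Perceived change and self-rated oral health:** the analysis is unspecified. It would be wrong to say that the plan assigns them to unadjusted tests.

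The change is worth making, but it does not bear on the clinical or OHIP-14 results.

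**What to change.** - For user versus non-user comparisons of follow-up willingness and overall treatment satisfaction, specify ordinal logistic regression (binary where an item is dichotomised) with the demographic, smoking, education and treatment-history covariates already used for OHIP-14.
- For willingness, add the baseline willingness item and the item on confidence when a dentist recommends use. For satisfaction, add baseline OHIP-14.
- State how perceived change and self-rated oral health are analysed. If they are compared between groups, use the same model.
- Keep the unadjusted tests as descriptive, and report all these results as associations.

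**Cost.** A few extra models and some wording; the covariates are already collected. With 130 patients and sparse response categories there will be some loss of precision, and categories may need merging. The adjusted differences will probably be smaller than the unadjusted ones.
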